1.5. Randomization and Blinding

Stratification

Dynamic randomization (ie, covariate-adjusted randomization) will be used to maintain balance between treatment groups with respect to the following stratification factors: AHA background (ie, diet and exercise only, metformin monotherapy, insulin monotherapy, or combination of metformin and insulin) and age group [≥ 10 to <15 years old, ≥ 15 to <18 years old]. The stratification process will be handled after logging on to the IWRS being used for the study.

Randomization

In dynamic randomization, a new subject is sequentially assigned to a particular treatment group by taking into account the specific covariates and previous assignments of subjects. This approach uses the method of minimization by assessing the imbalance of sample size among the covariates listed above. On Day 1, subjects will be randomized to 1 of 2 treatment groups based on a computer-generated dynamic randomization algorithm prepared by or under the supervision of the sponsor before the study. This approach seeks to maintain balance between treatment groups with respect to the AHA background and age group. The goal is to have at least 30% of randomized subjects that will be ≥ 10 to <15 years of age, 30% to 75% of participants will be female, and at least 20% in both age subsets (10 to <15 years, and ≥ 15 to <18 years) will be male, and 30% of participants that will have ethnicity and life-style comparable to Europe.

Re-randomization

At Week 12, subjects' glycemic status will be assessed by a central laboratory HbA_{1c} . Following the review of the Week 12 unmasked HbA_{1c} results and the Week 12 eGFR value, the following will occur:

- Subjects with HbA_{1c} value <7.0% or eGFR <60 mL/min/1.73 m2 will not be undergoing re-randomization and instead will be continuing their current treatment assignment (ie, canagliflozin 100 mg or matching placebo) for the remainder of the study.
- Subjects with HbA_{1c} value \geq 7.0% and eGFR \geq 60 mL/min/1.73 m2 will be re-randomized in a 1:1 ratio (in a blinded fashion via IWRS) to either.
 - remain on their original treatment assignment (ie, canagliflozin 100 mg or matching placebo) or
 - up-titrate canagliflozin 100 mg to 300 mg (or matching placebo). In order to keep the study blind, subjects randomized to the placebo group will undergo a mock up-titration.

Blinding

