- The primary efficacy endpoint will be analyzed using a mixed model for repeated measures (MMRM) based on restricted maximum likelihood. The analysis will use the observed data and will include the fixed, categorical effects of treatment, stratification factors (ie, background AHA and age group), visit, and treatment-by-visit interaction, as well as the fixed,

continuous covariates of baseline and baseline-by-visit interaction. An unstructured covariance will be used to model the within-patient errors. In case the model does not converge using the unstructured covariance then alternative covariance structures (such as compound symmetry and AR(1)) will be considered.

• The change from baseline in HbA_{1c} will be analyzed using an ANCOVA model with treatment and the stratification factors as fixed effects and baseline HbA_{1c} value as a covariate. The treatment differences in the least-squares means and the 2-sided 95% CI will be estimated based on this model. The last observation carried forward (LOCF) method will be applied when the Week 26 values are missing.

In addition, based on the FAS with the data collected up to Week 26, the following supportive analysis will be performed:

- A re-randomization test (Proschan 2011) (utilizing the MMRM) will be used to determine the p-value for the treatment comparison of the primary efficacy endpoint (ie, comparing all subjects who are randomized to canagliflozin to all subjects who are randomized to placebo). The re-randomization test will fix the observed HbA_{1c} data, regenerate treatment assignments for the entire study using the same minimization algorithm employed in the study and compute the test statistics corresponding to the treatment comparison. This process will be repeated at least 1,000 times. The p-value for the treatment comparison will be defined as the proportion of re-randomized studies whose test statistic for that comparison is at least as extreme as that of the original treatment assignment.
- A supportive analysis of the primary endpoint will be conducted based on the 26-week PP analysis set using the same mixed model with repeated measures as in the sensitivity analysis.

Subgroup Analyses

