5.3.2. Analysis Methods

The estimands for the secondary endpoints are the same as for the primary efficacy endpoint except for the variable.

Continuous endpoints (except for triglycerides) will be analyzed with an MMRM model as described before in the FAS population. For the endpoints with post-baseline assessments taken only at Week 26 and Week 52, an analysis of covariance (ANCOVA) model similar to the primary efficacy endpoint will be used at Week 26. The least-squares means for the treatment comparisons and their 2-sided 95% confidence intervals will be estimated based on this model. The analysis of percent change in triglycerides may be based on nonparametric methods (given the anticipated skewed nature of this parameter) or alternative methods.

The categorical secondary efficacy endpoint of maintaining HbA_{1c} <7.0% (and HbA_{1c} <6.5% and HbA_{1c} <7.5%) will be analyzed longitudinally using a generalized linear mixed model in the FAS population. The model will include the fixed, categorical effects of treatment, stratification factors (ie, background AHA and age group), visit, and treatment-by-visit interaction, as well as the fixed, continuous covariates of baseline and baseline-by-visit interaction. An unstructured covariance will be used to model the within-subject errors. The odds ratio and 2-sided 95% CI for the treatment comparisons at Week 26 (canagliflozin compared to placebo) will be estimated based on this model. It is possible that the generalized linear mixed model may fail to converge for the binary secondary efficacy endpoint of the proportion of subjects with HbA_{1c} <7.0% (and HbA_{1c} <6.5% and HbA_{1c} <7.5%) due to few subjects meeting the threshold. In this case, a logistic regression model will be used. The model will include treatment and stratification factor as fixed effects, and baseline HbA_{1c} value as a covariate. This alternative approach will be applied on the LOCF data at Week 26/Week 52 and the observed data by visit. Odds ratios and the 2-sided 95% CIs for the treatment comparisons will be derived from the model.

The time to event data (e.g., time to receiving rescue therapy or discontinuing due to need for rescue therapy) will be plotted using the KM method. The difference in proportion of subjects receiving rescue therapy or discontinuing due to need for rescue therapy between canagliflozin and placebo with 95% confidence intervals will be provided.

22

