5.4.2. Analysis Methods

The comparisons by dose (canagliflozin 100 mg without up-titration after Week 12 and canagliflozin 100 mg up-titrate to 300 mg after Week 12) to placebo will be tested for reference purpose by using the weights in the analyses described below.

- When comparing the subjects who initially receive canagliflozin 100 mg with no dose increase to 300 mg to placebo: All subjects start with a weight of 1. After Week 12, subjects with an $HbA_{1c} \ge 7.0\%$ and eGFR $\ge 60 \text{ mL/min}/1.73\text{m}^2$ who are re-randomized to continue canagliflozin 100 mg will have a weight of 2. The subjects who are re-randomized to up-titrate to canagliflozin 300 mg will have a weight of 0.
- When comparing the subjects who initially receive canagliflozin 100 mg followed by a dose increase to 300 mg to placebo: All subjects start with a weight of 1. After Week 12, subjects with an HbA_{1c} ≥7.0% and eGFR ≥60 mL/min/1.73m² who are re-randomized to continue canagliflozin 100 mg will have a weight of 0 and those who are re-randomized to up-titrate to canagliflozin 300 mg will have a weight of 2.

Given that lipids are only collected at baseline, Week 26 and Week 52, the percent change in lipid parameters (except for triglycerides) will be analyzed using an analysis of covariance at Week 26 and at Week 52 with LOCF applied when the Week 26 or Week 52 values are missing. The model will be similar to the supportive approach listed in Section 5.2.3. The percent change in triglycerides will be analyzed using nonparametric methods as outlined below given its skewed nature. A Wilcoxon rank sum test will be performed to compare canagliflozin to placebo. Additionally, the Hodges-Lehman estimator for the difference in the medians and the distribution-free confidence intervals based on the Wilcoxon rank sum test (Hollander 2013) will also be provided.

The change from baseline in SBP and DBP will be analyzed using an MMRM model similar to the one used to analyze the primary efficacy endpoint.

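### The triglyceride comparison uses a valid but unadjusted Wilcoxon test, which gives up some precision on a supportive endpoint that baseline and strata adjustment would recover

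*SAP*

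**What the plan says.** SAP 5.4.2 separates triglycerides from the other lipids because of skewness: "The percent change in triglycerides will be analyzed using nonparametric methods as outlined below given its skewed nature". The method is a two-group comparison, "A Wilcoxon rank sum test will be performed to compare canagliflozin to placebo", reported with "the Hodges-Lehman estimator for the difference in the medians and the distribution-free confidence intervals". No covariate or stratification is mentioned.

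In the same paragraph, percent change in the other lipids "will be analyzed using an analysis of covariance at Week 26 and at Week 52 with LOCF applied", with a model described as similar to the supportive approach of section 5.2.3. The matching model there is an "ANCOVA model with treatment and the stratification factors as fixed effects and baseline HbA_{1c} value as a covariate"; for a lipid, the natural reading is that the lipid's own baseline replaces HbA1c. The strata are "AHA background (ie, diet and exercise only, metformin monotherapy, insulin monotherapy, or combination of metformin and insulin) and age group" (SAP 1.5), balanced by minimization.

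SAP 5.3.2 is looser: "The analysis of percent change in triglycerides may be based on nonparametric methods", or on unnamed alternatives. Protocol 11.3.3 has similar wording and leaves the detail to the SAP. Neither document names a stratified Wilcoxon test, a rank ANCOVA or a log-scale model. SAP 5.1.1 calls the secondary endpoints supportive and keeps them out of the testing sequence.

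**The concern.** The other continuous efficacy endpoints are modelled with a baseline term and the stratification factors. Triglycerides alone lose both, and the only reason given is skewness. Skewness is a reason to use ranks or logs, but not a reason to drop covariates, since either approach can carry them.

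Dividing by baseline does not remove its influence. With equal variances on the log scale, log change correlates with log baseline at −√((1−ρ)/2), where ρ is the baseline to follow-up correlation. That is −0.55 at ρ = 0.4, −0.39 at 0.7 and −0.22 at 0.9. This predictable variation stays in the comparison as noise.

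No formal hypothesis test is planned for this endpoint, so its useful product is the estimate and interval, and the interval is what widens. There is also a labelling point. The Hodges-Lehmann estimate is the median of the pairwise between-arm differences. It equals a difference in medians under a pure shift, which skewed percent changes need not follow.

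**Working it through.** **The plan's own figure.** The only sizing in the documents is for HbA1c (SAP 1.4). The mean effect is 0.5×0.5 + 0.25×0.4 + 0.25×0.5 = 0.475, with SD 0.9 and 2-sided alpha 0.05. At 66 per group the noncentral t gives 85.3% power, and 66×1.10 = 72.6, rounded up to 73. Both match the SAP. No precision or power figure is given for triglycerides, so 66 per arm is carried forward and everything else below is assumed.

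**Gain from baseline.** Let V be the variance of log triglycerides at each visit.
- Unadjusted log change: variance 2V(1−ρ).
- ANCOVA residual: variance V(1−ρ²).
- Ratio: (1−ρ²)/(2(1−ρ)) = (1+ρ)/2. The standard error narrows by 1 − √((1+ρ)/2).

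| Assumed ρ | Variance ratio | SE narrower by |
|---|---|---|
| 0.4 | 0.70 | 16% |
| 0.5 | 0.75 | 13% |
| 0.6 | 0.80 | 11% |
| 0.7 | 0.85 | 8% |
| 0.9 | 0.95 | 2.5% |

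**Does the gain survive a change of shape?** Simulated power (%), with 66 per arm, log SD 0.55, true ratio 0.80 and adjustment for baseline only. The log values are either normal or heavy-tailed (t with 4 degrees of freedom, same SD).

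| Assumed ρ | Wilcoxon, normal | Rank ANCOVA, normal | Log-ANCOVA, normal | Wilcoxon, heavy | Rank ANCOVA, heavy |
|---|---|---|---|---|---|
| 0.4 | 55 | 69 | 72 | 70 | 82 |
| 0.5 | 61 | 72 | 74 | 78 | 87 |
| 0.6 | 71 | 80 | 83 | 85 | 91 |
| 0.7 | 84 | 88 | 89 | 93 | 95 |

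Under heavy tails, log-ANCOVA reached 78% at ρ = 0.5 (Wilcoxon 78%) and 89% at ρ = 0.7 (Wilcoxon 93%). Its advantage vanishes or reverses. Rank ANCOVA beat the plain Wilcoxon under both shapes.

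**Gain from strata.** A second simulation used 66 per arm, log SD 0.5, eight strata balanced across arms, and an effect rescaled at each ρ. It compared Wilcoxon with rank ANCOVA on baseline plus strata at ρ = 0.3, 0.5, 0.7 and 0.9.
- Strata with no effect: 75 vs 91, 77 vs 87, 78 vs 84 and 77 vs 80%.
- Strata explaining about 10% of the variance: 74 vs 90, 73 vs 86, 74 vs 82 and 73 vs 79%. Here the Wilcoxon test was conservative, with type I error of 3.3 to 4.0% against 4.5 to 5.2% for the adjusted analysis.

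**The case against.** The strongest reply is that this is a choice between valid methods. Randomization justifies the Wilcoxon test, minimization balances the strata, and a rank method for a skewed lipid is reasoned and stated. All of that stands. A reader might infer bias or an inflated error rate; nothing in the documents supports that, and the simulations show at most mild conservatism.

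A reader might also infer that log-ANCOVA should simply replace the Wilcoxon test, or that precision is being discarded at no cost. The documents do not support either. They give no tail shape, and under heavy tails log-ANCOVA loses its edge. It also changes the reported summary from percent change to a ratio. Adjustment is free in data, since the covariates are already collected, but not in presentation.

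Power overstates the stakes. The ratio of 0.80 comes from neither document; at 0.90, under the log-normal set-up, Wilcoxon against log-ANCOVA is only 16 vs 21, 18 vs 24 and 27 vs 32% at ρ = 0.4, 0.5 and 0.7. Interval width is the fairer measure for a supportive endpoint. It is also too strong to say that baseline is ignored, because percent change divides by it; it is omitted as a covariate.

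One part of the reply fails. The room that SAP 5.3.2 leaves for other methods specifies no adjusted analysis, and section 5.4.2 is firm about the unadjusted one.

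**Conclusion.** The point holds as a modest loss of precision. The triglyceride analysis omits the baseline covariate and the strata that the plan uses for other continuous efficacy endpoints. Baseline adjustment would narrow the standard error by about 8 to 16% for correlations of 0.7 down to 0.4, and by almost nothing near 0.9. These figures rest on assumed correlations and on equal variances on the log scale. Prognostic strata would add to the gain by an amount that the documents do not allow one to fix.

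The planned test remains valid. The primary result, the metformin-subset test and the family-wise error rate are untouched. The Hodges-Lehmann label is a wording correction that changes no number.

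**What to change.** Amend SAP 5.4.2 so that the Week 26 and Week 52 triglyceride comparisons are adjusted:
- **Test:** rank ANCOVA of percent change on treatment, baseline triglycerides and the stratification factors. This held its advantage under heavy tails.
- **Adjusted estimate:** ANCOVA on log triglycerides with treatment, strata and log baseline, reported as a geometric mean ratio with 95% CI.
- **Unadjusted sensitivity summary:** keep the Wilcoxon test and Hodges-Lehmann interval, labelled as the median of pairwise differences.
- **Consistency:** make section 5.3.2 name the same method as section 5.4.2. The same edit could state how missing triglyceride values are handled, since LOCF is stated only for the other lipids.

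The cost is a few SAP sentences and no new data. The adjusted estimate will be a ratio of geometric means, not a difference in percent change, so it will not sit on the same scale as the other lipids. Rank ANCOVA does not itself produce an effect estimate on the percent-change scale, which is why the log-scale model is needed beside it.

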6. SAFETY

All safety analyses and summaries will be based on the safety analysis set (Section 2.2.2). Safety data will be analyzed according to the predominant treatment received, in the event that a subject

received a treatment other than that to which they were randomly assigned to receive. The predominant treatment is defined as the treatment to which the subject was exposed for the greatest duration during the double-blind treatment phase.

There will be no imputation of missing values for clinical laboratory test results, vital signs measurements in the safety analyses and there will be no hypothesis testing for results from safety analyses.

6.1. Adverse Events

Adverse events will be summarized for the 26-week core double-blind treatment period and for the 52-week double-blind treatment phase separately. AEs will be coded using the latest version of the Medical Dictionary for Regulatory Activities (MedDRA) at the time of database lock. Therefore, the preferred terms presented in Attachment 2 may be updated to reflect such updates. A treatment-emergent AE (TEAE) is defined as an adverse event with an onset after the initiation of double-blind study medication and before the last study medication date + 30 days. AEs with a start date prior to initiation of double-blind study medication which are subsequently reported to have either an increase in intensity or change in attribution in relationship to study medication (ie, no attribution to possible, probably, very likely) after the initiation of double-blind study medication will also be considered as TEAEs. Treatment-emergent AEs before the initiation of rescue therapy and TEAEs regardless of rescue therapy will be summarized separately for the 26-week core double-blind treatment period and for the 52-week double-blind treatment phase.

The overall incidence (ie, number and percent of subjects with one or more AE in each category) of AEs, AEs leading to discontinuation of study medication, drug-related AEs, drug-related AEs leading to discontinuation of study medication, serious AEs, serious AEs leading to discontinuation of study medication, serious drug-related AEs, serious drug-related AEs leading to discontinuation of study medication, serious drug-related AEs, serious drug-related AEs leading to discontinuation of study medication, serious drug-related AEs, serious drug-related AEs leading to discontinuation of study medication and deaths, will be summarized by treatment group.

AEs by SOC (ie, number and proportion of subjects with one or more AEs within a SOC) will be summarized by treatment group.

For each AE, the percentage of subjects who experienced at least one occurrence of the given event will be provided by preferred term, grouped by SOC, and presented by treatment group. In addition, the incidence of AEs (by preferred term, grouped by SOC, and presented by treatment group) will also be summarized by severity (by each designation, and pooling mild or moderate), by the relationship to study medication, by the action taken regarding the study medication, as well as by the outcome. The relationship to study medication will be presented by 2 categories: related (which includes possibly related, probably related and very likely related, as reported by the investigator) and not related (which includes not related and doubtfully related, as reported by the investigator), as well as by individual designation.

Listings will also be generated for deaths, SAEs, and AEs leading to discontinuation.

As a screening tool, the 95% CIs for percentage difference between canagliflozin and placebo will be provided for the AEs which are reported in at least four or more subjects in any treatment group.

Four (rule-of-4) was chosen based on the recommendation from the Safety, Planning, Evaluation, and Reporting Team (SPERT) (Crowe 2009) for studies with less than 400 subjects in each treatment group. No multiplicity adjustment will be applied. The exclusion of "0" in the 95% CI around the difference in incidence (canagliflozin compared to placebo) for a particular AE does not necessarily imply that the higher incidence is related to drug. The intent of providing the 95% CI is as a filter to identify AEs that require additional assessment.

Adverse events that are identified by the above screening procedure will be subject to further evaluation. The additional assessment may include some or all of the following:

- 1. Investigator assessed relationship of AE to study drug, investigator assessed intensity of AE.
- 2. Time to AE relative to start of double-blind study medication, duration of AE, action taken on study drug/occurrence of AEs leading to discontinuation.
- 3. Other relevant safety information such as observations in other canagliflozin trials, observations in trials of other members of the SGLT2 inhibitor class, biological plausibility of the AE as related to SGLT2 inhibition or to canagliflozin.

All hypoglycemic events will be reported on an eCRF page specific for hypoglycemia. If the hypoglycemia event is considered to be an AE/SAE in the opinion of the investigator, the event was also to be recorded on the AE/SAE eCRF page. Hypoglycemia as AEs/SAEs will be presented in the tabulation of AEs described above. All additional analysis of hypoglycemia events (Section 6.1.2) will be based on results collected using the hypoglycemia eCRF. Reconciliation will be conducted to assure that all hypoglycemia events reported as AEs are also recorded on the hypoglycemia eCRF form; however, hypoglycemia events reported on the hypoglycemia eCRF do not have to be reported as an AE of hypoglycemia as this determination is left to the investigator's clinical judgement.

6.1.1. Selected Adverse Events for Additional Analysis

To support the additional assessment of particular categories of AEs, such as vulvovaginal candidiasis, balanitis or balanoposthitis, urinary tract infections (UTIs), volume depletion, hepatic injury, renal impairment/renal failure, hypersensitivity, venous thromboembolic event, photosensitivity, and malignancy, groupings of selected preferred terms will be created. A blinded review prior to database lock will be performed to assure that no reported term suggestive of the AE of interest is omitted. The list of preferred terms that are to be combined for assessment of each of the pre-specified AEs is provided in Attachment 2. Given the planned sample size of the study (ie, 146 subjects overall), listings may be provided instead of summary tables for any selected AEs below that are reported with low incidence (ie, <5%).

Fracture events identified by the investigator or the sponsor for meeting the criteria pre-specified in the charter will be sent to an independent fracture adjudication committee to confirm that events were fractures, to determine fracture location (anatomic region) and type (low trauma or not). Summary of the fracture events will be based on the adjudicated events of fracture.

Diabetic ketoacidosis (DKA) identified by investigator or the sponsor for meeting the criteria prespecified in the charter will be sent to an independent DKA adjudication committee. Summary of the DKA events will be based on the adjudicated events of DKA.

Pancreatitis identified by investigator or the sponsor for meeting the criteria pre-specified in the charter will be sent to an independent pancreatitis adjudication committee. Summary of the pancreatitis events will be based on the adjudicated events of pancreatitis.

Lower extremity amputation will be recorded on a dedicated amputation case report form page. Summary of the lower extremity amputation will be based on the case report form page.

